2.1 General objective

Develop an application for the two most popular *smartphone platforms* (Google Android and Apple iPhone) aimed at treating SAH, with tools aimed at medication adherence, blood pressure monitoring, monitoring and promotion of physical activity and lifestyle habits healthy subjects of Brazilians with SAH.

2.2 Specific Objectives

The specific objectives of the study will be:

a) develop a prototype application aimed at treating patients with SAH, including tools to improve medication adherence, monitor blood pressure values, monitor and promote physical activity and healthy lifestyle habits;

b) test the effectiveness of this application on laboratory systolic and diastolic blood pressure, adherence to drug treatment, habitual physical activity and lifestyle in hypertensive adults.

c) test the usability of this application on hypertensive adults.

3 Materials and methods

The study will be developed in three stages, according to the objectives outlined. Initially, a prototype of a cellphone application will be developed to help Brazilian adults diagnosed with SAH, with tools related mainly to medication adherence, promotion of physical activity and monitoring of blood pressure values, in addition to health tips (food, smoking, alcoholism and stress management). Subsequently, this prototype will be made available to a group of adult hypertensive patients so that the effectiveness of this application can be tested on laboratory blood pressure values, medication adherence and lifestyle aspects, including physical activity and, subsequently, physical activity. Application usability will be tested. Subsequently, after making the necessary adjustments, the application will be made available on the Apple iTunes and Google Play platforms and disseminated in groups of Basic Health Units and in the media (advertisements on television, newspaper, radio). From there, the number of downloads and the grade assigned to user reviews (one, two, three or

four stars) will be evaluated, according to the user's sociodemographic characteristics (gender, age, place of residence).

App Development

3.1 General Description

The main focus of the application is to assist in the treatment of patients with SAH. The application will address the components of adherence to medication use, blood pressure monitoring and promotion/monitoring of physical activity. In addition, health education tips will be provided, including guidelines for reducing sodium consumption, adopting an adequate and healthy diet, controlling body weight, moderate alcohol consumption and stress management, in accordance with the recommendations of the main guidelines related to the theme ^{1, 3}.

After downloading, patients must manually enter demographic data (date of birth, sex), their body mass and height, information regarding the use of the drugs used, the presence of comorbidities (diabetes, dyslipidemia, chronic kidney disease, coronary artery disease, peripheral arterial disease, among others). In addition, the user must enter data related to their lifestyle, including information about: physical activity, nutrition, alcohol consumption, tobacco use, stress and relationships, according to an adapted version of the Fantastic lifestyle.

Based on this information entered by the patient (*input*), the application will issue reminders: a) for the use of the medication(s), according to the time registered by the patient, daily; b) to perform blood pressure measurements. The patient will be instructed to take blood pressure measurements while sitting, in a calm environment, after five minutes of rest, with the bladder emptied and there is at least 30 minutes of abstention from food, cigarettes and/or alcoholic and caffeinated beverages. Such measured BP values must be entered in the application and, if a BP level above the recommended values is identified, the insertion of the importance of the correct use of antihypertensive medication and adoption of a healthy lifestyle will increase. It will also be suggested that you consult your doctor for possible medication adjustments.

In addition, the user will be given the possibility to self-monitor their physical activities and, based on this information, the application will generate

feedback informing whether or not the user has reached the recommendations currently in force^{17,18}. If the user does not meet the recommendations throughout the week, illustrative messages or videos will be generated with stimuli and guidelines for the patient to increase their level of physical activity, according to such recommendations. Illustrative messages or educational videos will also be made available with tips on healthy living habits, including recommendations for body weight control, reducing sodium consumption, adopting healthy eating habits, stress control and smoking cessation, as recommended by the main guidelines related to thematic^{1,3}.

Reports for the patient regarding blood pressure values and physical activity will be available, showing the evolution over time. For programmers and researchers, these same reports will also be generated, in addition to reports with application usage statistics and general user characteristics (*business intelligence*), so that, with this information, the system can be feedback.

Patients will be able to designate family members and/or friends to have access to the data captured and generated by the application, so that these people can provide social support for the treatment of hypertensive patients. In addition, a communication channel will be opened between patients that the application identifies in closer locations, in case the patient wants to share doubts, challenges and achievements.

3.2 Effectiveness testing

3.2.1 Participants

This stage of the study will involve the performance of a randomized and controlled clinical trial that will be conducted at the Sports Center of the Federal University of Santa Catarina, Florianópolis, SC. Based on a previous behavior change study¹⁹, taking systolic blood pressure as a reference, taking into account an effect size of 0.8, power of 80% and alpha error of 0.05, the estimated sample size is 52 participants (26 per group). The recruitment of these participants will be based on the dissemination of the research in the local media (radio, newspapers, internet) and in social groups, distribution of pamphlets and posting of posters in the vicinity of the evaluation sites.

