3.2.2 Screening

As inclusion criteria, participants must be over 18 years old, have a clinical diagnosis of SAH³, have been using antihypertensive medication for more than three months, and cannot be involved in the regular practice of physical activities. In addition, participants must have a *smartphone*, they must not have cognitive disabilities that limit the understanding and use of an application and/or physical limitations that make it difficult to practice physical activities. Changes in the type and/or dose of antihypertensive drugs used during the study will be considered as exclusion criteria.

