3.2.3 Randomization

After the pre-intervention assessments, participants will be randomized into two groups: app group (GA) and control group (CG). This randomization will be performed in blocks, according to sex and pre-intervention blood pressure, from a table of random numbers, by researchers who are not directly involved with the recruitment of participants and with data collection.

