3.2.4 Experimental Design

Participants will be submitted, before the start of the intervention (pre-intervention), to laboratory blood pressure assessments, adherence to drug treatment, physical activity and lifestyle. Afterwards, the GC will participate in an informative lecture on healthy habits and general aspects of SAH control and treatment, while the GA will be submitted to the use of the application for eight weeks. At the end of these eight weeks of intervention (post-intervention), the participants of both groups will be reassessed in all the items analyzed at the pre-intervention moment. It is noteworthy that the researchers involved with the evaluations and data analysis will be blinded regarding the randomization of the participants.

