3.2.12 Statistical analysis plan (SAP)

Initially, the normality and homogeneity of variance will be analyzed using the Shapiro-Wilk and Levene tests, respectively. For data that do not have a normal distribution, logarithmic transformation will be performed. Student 's t test for independent samples and the chi-square test will be used to compare the groups at the pre-intervention moment, regarding continuous and categorical variables, respectively.

For the Intra and inter-group comparisons of quantitative and qualitative variables, the method of generalized estimation equations will be used (group: GA and GC; time: pre and post-intervention assessments; interaction (group vs. time), after confirming the appropriate assumptions. In all analyses, when a significant effect is verified, the Newman-Keuls post-hoc test will be used, with a P value <0.05 being considered significant.

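### Recruitment is set at the bare t-test minimum of 52 with no allowance for losses; adjusting systolic pressure for baseline would give some reserve without enrolling more people

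*Combined protocol and SAP*

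**What the plan says.** - **Size (3.2.1).** The trial is sized "taking systolic blood pressure as a reference", with "an effect size of 0.8, power of 80% and alpha error of 0.05, the estimated sample size is 52 participants (26 per group". The next sentence turns to recruiting that number: "The recruitment of these participants will be based on the dissemination of the research in the local media". No larger enrolment target appears.
- **Losses.** No section gives an expected loss rate, an inflated target, an analysis population or a rule for missing data.
- **Follow-up (3.2.4).** There is one reassessment: "At the end of these eight weeks of intervention (post-intervention), the participants of both groups will be reassessed".
- **Drug changes (3.2.2).** "Changes in the type and/or dose of antihypertensive drugs used during the study will be considered as exclusion criteria". The plan does not say whether a randomised participant whose drugs change leaves the analysis.
- **Baseline (3.2.3).** "After the pre-intervention assessments, participants will be randomized into two groups", and "This randomization will be performed in blocks, according to sex and pre-intervention blood pressure". Baseline pressure is therefore known for everyone before allocation.
- **Analysis (3.2.12).** Generalised estimating equations with "group: GA and GC; time: pre and post-intervention assessments; interaction (group vs. time"). Baseline SBP enters as a repeated outcome, not as a covariate.

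**The concern.** A number that only just reaches 80% power with complete data leaves nothing for anyone who misses the single eight-week visit, and possibly nothing for those whose drugs change. If SBP then shows no significant difference, readers need to know what effect the trial could have detected, and the plan would not tell them.

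The planned test does not settle the matter. Its power depends on two quantities that the plan does not give: whether 0.8 is in SDs of a single SBP value or of the change, and the correlation r between pre and post values. Meanwhile the baseline SBP already collected could supply precision that the group-by-time contrast leaves unused.

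**Working it through.** **Inputs.** From 3.2.1: d = 0.8, power 80%, alpha 0.05, 26 per group. Inferred: two-sided t-test, since it reproduces 52. Assumed, because the documents give no figure: the number of losses (4, 6 or 10, split equally) and r (mainly 0.3 to 0.7).

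**1. The plan's own figure.** Noncentral t with n per group, noncentrality d√(n/2), df 2n − 2.
- n = 26: 0.8 × √13 = 2.884, df 50, power 80.7%.
- n = 25: 0.8 × √12.5 = 2.828, df 48, power 79.1%.

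So 26 per group is the minimum. A two-sided normal approximation gives 25 per group; a one-sided t-test gives 21.

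**2. Losses under that calculation.** Power is 79.95% with 51 analysed, 77.4% with 48, 75.6% with 46 and 71.6% with 42. The effect detectable with 80% power is 0.79 SD at 52, 0.84 at 46 and 0.89 at 42.

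**3. The planned group-by-time contrast.** With two time points and complete data this is a difference in mean change.
- If 0.8 is in single-value SDs, the standardised effect is 0.8/√(2(1 − r)): 0.676, 0.800 and 1.033 at r = 0.3, 0.5 and 0.7.
- If 0.8 is in change SDs, it is 0.8 at any r, and power equals that of the t-test in step 2.

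**4. Post-intervention SBP adjusted for baseline.**
- Single-value scale: 0.8/√(1 − r²) = 0.839, 0.924 and 1.120 at r = 0.3, 0.5 and 0.7.
- Change scale: 0.8 × √(2/(1 + r)) = 0.992, 0.924 and 0.868.
- df is 2n − 3. The variance of the group difference is multiplied by 1 + F/(2n − 2), and power is averaged over F(1, 2n − 2), to allow for chance baseline imbalance under simple randomisation. Blocking on baseline pressure should reduce imbalance, so these figures are slightly conservative.

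**5. Results.** Power (%); triplets are r = 0.3 / 0.5 / 0.7.

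| Analysed | Implied t-test; also group by time on change scale | Group by time, single-value scale | Adjusted, single-value scale | Adjusted, change scale |
|---|---|---|---|---|
| 52 | 80.7 | 66.7 / 80.7 / 95.5 | 83.5 / 89.8 / 97.5 | 93.5 / 89.8 / 85.9 |
| 48 | 77.4 | 63.0 / 77.4 / 93.8 | 80.3 / 87.2 / 96.3 | 91.4 / 87.2 / 82.9 |
| 46 | 75.6 | 61.1 / 75.6 / 92.9 | 78.5 / 85.7 / 95.6 | 90.2 / 85.7 / 81.1 |
| 42 | 71.6 | 57.1 / 71.6 / 90.4 | 74.4 / 82.2 / 93.7 | 87.2 / 82.2 / 77.3 |

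**6. Where the adjusted test keeps 80% on both scales.** r of about 0.29 to 0.83 at 48 analysed, 0.36 to 0.75 at 46, and 0.46 to 0.58 at 42.

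**7. Detectable effect at 42 analysed, in single-value SDs, at r = 0.3, 0.5 and 0.7.** Group by time: 1.05, 0.89 and 0.69. Adjusted: 0.86, 0.78 and 0.64.

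**8. Where adjustment loses.** The adjusted error variance is (1 − r²)/(2(1 − r)) = (1 + r)/2 of the change-score variance, so it is smaller whenever r is below 1. After the lost degree of freedom and the imbalance penalty, on the change scale the two powers cross at r of about 0.96 with 52 analysed and 0.95 with 42. Beyond that, adjustment costs at most about 1.2 points. At r = 0 on the single-value scale it has 79.9% at 52 analysed, so it gives no reserve there.

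**The case against.** The strongest reply is that the loss figures belong to a t-test the plan never names, while the test it does plan may already have room. On the single-value scale at r = 0.7, group by time keeps about 90% power with 42 analysed, and it stays at or above 80% there once r reaches about 0.59. Section 3.2.7 averages at least three readings on each of two days, which should raise r and narrow the gain from adjustment. This stands as a limit: no deficit is proved for the planned test. But that room exists only on one reading of the 0.8. On the change scale the planned test has the t-test's power at every r, and so no reserve.

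A second reply is that a change of model does not supply a loss allowance, and that the direct remedy is to enrol more: 52/(1 − 0.10) gives 58 and 52/(1 − 0.20) gives 65. It is true that adjustment covers only some losses and that the amount depends on r. On the change scale at r = 0.85, even four losses leave 79.6%, against 77.4% unadjusted. This is why the power statement must be rewritten as well, with a figure below 80% if that is what results. Raising enrolment is possible but costs participants; adjustment does not.

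A third reply is that both contrasts are valid under randomisation, that the loss counts are assumed, and that one loss hardly matters. All of that is correct. The case for adjustment is precision at almost no cost, not invalidity of the plan.

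Finally, if participants whose drugs change are dropped, bias may matter more than power, because section 3.1 has the app suggest a medical consultation about medication. Adjustment does not remove that bias. Sections 3.1 and 3.2.2 need to be reconciled on this point.

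**Conclusion.** The concern holds, as something the sponsor should change rather than a flaw that invalidates the trial. The figure of 52 is correctly computed but has less than one percentage point of spare power, and nothing in the plan provides for losses. Comparing SBP adjusted for baseline is more powerful than the planned contrast on either scale unless r exceeds about 0.95. With everyone analysed, it raises power by 16.8, 9.1 and 2.0 points at r = 0.3, 0.5 and 0.7 on the single-value scale (83.5 − 66.7, 89.8 − 80.7, 97.5 − 95.5), and by 12.8, 9.1 and 5.2 points on the change scale (93.5, 89.8 and 85.9, each less 80.7).

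This rests on the inferred two-sided t-test and on assumed losses and r. The reserve is useful but limited, and with ten losses it is secure on both scales only in a narrow band of r.

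**What to change.** 1. **Section 3.2.12.** For SBP, replace the group-by-time test with a between-group comparison of post-intervention SBP adjusted for baseline SBP. The other outcomes can stay as planned.
2. **Section 3.2.1.** Keep 52 recruited. Restate the power, or the detectable effect, under that test for the number expected to be analysed. Give the assumed loss, the scale of the 0.8 and the assumed r, with reasons. If the result is below 80%, say so.
3. **Sections 3.2.2 and 3.2.12.** State whether participants who meet the drug-change criterion after randomisation leave the analysis, so that the expected number analysed is defined.

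**Cost.** A small change to one model and a rewritten power statement that may look less favourable. There are no extra participants, visits or measurements.

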3.2.2 Screening

As inclusion criteria, participants must be over 18 years old, have a clinical diagnosis of SAH³, have been using antihypertensive medication for more than three months, and cannot be involved in the regular practice of physical activities. In addition, participants must have a *smartphone*, they must not have cognitive disabilities that limit the understanding and use of an application and/or physical limitations that make it difficult to practice physical activities. Changes in the type and/or dose of antihypertensive drugs used during the study will be considered as exclusion criteria.

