3.2.5 Application group

Participants undergoing the GA will be instructed on how to *download* the application and how to use it. From there, all personal data must be entered into the application so that alerts, tips and incentives can be issued to each one, individually, as described in item 3.1 (application development).

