3.2.6 Control group

The GC, in turn, will participate in a single lecture, in the first week of the intervention, with basic guidelines related to the key points of the treatment of SAH, including the importance of medication adherence, monitoring of blood pressure values and/or capillary glucose, lifestyle modifications linked to physical activity, eating habits, smoking cessation, stress management and moderate alcohol consumption.

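### Participants whose antihypertensive drug or dose changes are excluded after randomisation, and only the app arm is prompted to seek such a change

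*Combined protocol and SAP*

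**What the plan says.** - **Exclusion rule (section 3.2.2, Screening).** "Changes in the type and/or dose of antihypertensive drugs used during the study will be considered as exclusion criteria". Treatment before entry has its own criterion in the same section: participants must "have been using antihypertensive medication for more than three months". The exclusion therefore looks forward, to changes after enrolment.
- **Timing (sections 3.2.3 and 3.2.4).** "After the pre-intervention assessments, participants will be randomized into two groups". The eight intervention weeks follow.
- **App arm (sections 3.1 and 3.2.5).** When a user enters a BP above the recommended values, the app responds: "It will also be suggested that you consult your doctor for possible medication adjustments". Section 3.2.5 applies the section 3.1 alerts to this arm: "all personal data must be entered into the application so that alerts, tips and incentives can be issued to each one, individually".
- **Control arm (section 3.2.6).** Controls "will participate in a single lecture, in the first week of the intervention". The lecture covers adherence, BP monitoring and lifestyle. No BP-triggered prompt and no advice to seek a medication adjustment is described.
- **Follow-up (section 3.2.4).** At eight weeks "the participants of both groups will be reassessed in all the items analyzed at the pre-intervention moment". Nothing is said about people whose drugs have changed.
- **Analysis (section 3.2.12).** For comparisons within and between groups, "the method of generalized estimation equations will be used", with group, time and their interaction. There is no analysis set, intention-to-treat statement or rule for excluded participants.

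**The concern.** The intervention prompts the event that removes a participant. It does so in one arm only, and the trigger is BP, the outcome used to size the trial. On the natural reading, the groups analysed are then no longer the groups randomised. Stratifying on baseline BP balances those who enter, not those who remain. Blinding of assessors and analysts does not prevent this selection either.

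The error could go either way. Removing app users with high readings would flatter the app. Removing users whose prompted adjustment brought their BP down would discard part of what the app achieved. The plan also leaves open whether exclusion means no week-8 measurement or only removal from the analysis, and whether an excluded person's baseline record stays in the model. That last choice changes the size of the bias considerably. Finally, the analysed number falls below the 52 on which the stated power rests.

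**Working it through.** **1. The plan's own figure.** Section 3.2.1 gives a standardised effect of 0.8, 80% power, alpha 0.05 and 52 participants. A two-sided two-sample t-test needs 25.52 per group, rounded up to 26, so the figure reproduces. Power at 26 per group is 80.7%. There is no allowance for exclusions.

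**2. Assumed inputs.** None of these is in the documents.

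- SBP has SD 15 mmHg at each time, so an effect of 0.8 corresponds to 0.8 × 15 = 12 mmHg.
- The correlation is 0.6 between baseline and on-study BP and between baseline and final BP. Between on-study and final BP, r is 0.6 or 0.8.
- A fraction q (30% or 40%) with the highest on-study BP are candidates for a drug change.
- A fraction p of candidates change: 50% or 70% in the app arm, 5% in control. A milder case uses 25% against 5%.
- The app has no true effect.

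Overall exclusion is p × q. In the app arm that is 0.5 × 0.3 = 15% to 0.7 × 0.4 = 28%. In control it is 0.05 × 0.3 = 1.5% to 0.05 × 0.4 = 2%. The mean analysed number is 26 × 0.85 = 22.1 down to 26 × 0.72 = 18.7 in the app arm, and about 25.5–25.6 in control.

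**3. Selection in each arm.** In SD units, the mean on-study BP of those who remain is m = −p·φ(z_q)/(1 − p·q), where z_q is the normal point cutting off the top fraction q and φ is the normal density.

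| Scenario | φ(z_q) | m, app | m, control | Difference D |
|---|---|---|---|---|
| q = 0.3; p = 0.5 v 0.05 | 0.3477 | −0.2045 | −0.0176 | −0.187 |
| q = 0.4; p = 0.7 v 0.05 | 0.3863 | −0.3756 | −0.0197 | −0.356 |
| q = 0.3; p = 0.25 v 0.05 | 0.3477 | −0.0940 | −0.0176 | −0.076 |
| q = 0.4; p = 0.25 v 0.05 | 0.3863 | −0.1073 | −0.0197 | −0.088 |

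**4. Bias in the group-by-time contrast.**

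*Both records of an excluded person removed.* Bias = (r − 0.6) × 15 × D.
- With r = 0.6 it is zero.
- With r = 0.8 it is 3 × (−0.187) = −0.6 to 3 × (−0.356) = −1.1 mmHg, at most 1.1/12 = 9% of the planned effect.
- In simulation (40,000 trials per scenario) a t-test on change rejected in 5–6% of trials.
- Milder case: 0 to 3 × (−0.088) = −0.3 mmHg.

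*Only the final record removed, baseline kept, independence working correlation.* Bias = r × 15 × D.
- The range is 0.6 × 15 × (−0.187) = −1.7 to 0.8 × 15 × (−0.356) = −4.3 mmHg.
- Fitted GEE (1,200 trials at each extreme scenario) gave −1.5 and −4.2 mmHg, with rejection of 7.3% and 17.3%.
- Milder case: about −0.7 to −1.0 mmHg.

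*The same with exchangeable working correlation.*
- Bias is about −0.5 to −2.5 mmHg, with rejection of about 5.5–10%.
- Milder case: −0.3 to −0.6 mmHg.

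The GEE rejection rates include some small-sample inflation from the robust standard error, so the excess over 5% is not all selection bias.

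**5. The opposite direction.** Suppose each drug change lowers final SBP by 10 mmHg (assumed). The true effect of assignment is then −10 × (0.15 − 0.015) = −1.4 to −10 × (0.28 − 0.02) = −2.6 mmHg. With both records removed, the analysis shows only 0 to −1.1 mmHg. Matched by scenario, 0.8 to 2.6 mmHg of real effect is lost.

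**6. Power at an effect of 0.8 (noncentral t).**

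| App v control analysed | Power |
|---|---|
| 26 v 26 | 80.7% |
| 24 v 26 (milder case) | 79.1% |
| 23 v 26 (milder case) | 78.2% |
| 22.1 v 25.6 | 76.9% |
| 21 v 25 | 75.3% |
| 19 v 25 | 72.8% |

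**The case against.** The strongest reply is that, on the natural reading, an excluded person leaves the analysis entirely. The bias under no effect is then 0 to −1.1 mmHg with near-nominal rejection, even under steep inputs. The larger figures need the baseline record to stay in the model. This is correct. The plan does not rule that handling out, but the smaller range should be taken as the leading case.

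The inputs are also steep: overall exclusion is 10 to 14 times higher in the app arm than in control. Controls hear about BP monitoring and are already on treatment, so their drugs may change too. Raising the control figure to 25% of candidates, against 50% in the app arm, cuts the bias at r = 0.8 to about −0.3 to −0.4 mmHg with both records removed. The independence range falls to −1.0 to −1.6 mmHg. Equal rates with equal dependence on BP would remove the bias. The documents establish a difference in prompting; a difference in drug-change rates is a likely consequence, not a certainty.

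It can also be said that holding medication constant isolates the behavioural effect. That is a recognisable aim, but dropping people on a post-randomisation event does not deliver it without further assumptions. Nor does GEE rescue the comparison, since it can use only the records that are collected and kept.

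These points limit the size that can be claimed. They do not remove the defect: following the rule as written breaks the randomised comparison.

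**Conclusion.** The concern holds and should be fixed before the trial runs. The rule, its mainly post-randomisation operation, the app-only prompt and the absence of an analysis set retaining these participants are all on the page. That exclusion will differ by arm and depend on BP is a probable inference.

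Size and sign are unknown. The millimetre and power figures illustrate assumed rates, correlations and an SD of 15 mmHg. The bias could be negligible under complete removal or several mmHg if baseline records are kept, and the loss of a real effect is as possible as a spurious gain. The case does not rest on any one figure. It rests on an effectiveness trial whose intervention can trigger removal from its own analysis, and on week-8 measurements that cannot be recovered if they are not taken.

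**What to change.** - Reconcile sections 3.1 and 3.2.2, which pull against each other. No view is taken here on how medication should be managed.
- State the estimand: the effect of assignment to the app, whatever medication changes occur.
- Remove on-study drug or dose change as a reason for exclusion from follow-up or analysis.
- Reassess every randomised participant at week 8, and define the main analysis set as all randomised participants in their assigned group.
- Record drug and dose changes and report them by arm.
- Keep the analysis without these participants only as a labelled sensitivity analysis, and say whether their baseline records remain in it.

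**Cost.** This is protocol and SAP wording. Section 3.2.4 already plans reassessment of both groups, so nothing is added to the planned schedule or sample. If exclusion had been meant to stop measurement, the retained people would need their two BP days and seven days of accelerometry after all. The main estimate will then include any effect of medication changes, which the by-arm report and the sensitivity analysis make visible. Enlarging the sample instead would restore power but leave the selection bias in place.
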